This pilot proposal is a randomized longitudinal single-blind sham-controlled intervention. Individuals with PSF will be randomly assigned to the sham or a-tDCS treatment group. Before and after five consecutive days of a-tDCS applied bilaterally over the left and right lower extremity motor cortex, PSF and nervous system and peripheral inflammation will be measured, similar to De Doncker et al. (2021). The tDCS treatment will consist of twenty minutes of 4 mA a-tDCS delivered via two carbon rubber electrodes placed inside sponge pads (1x1 tDCS, Soterix, USA). The current will be ramped up 4 mA over 30 seconds. Each electrode has a surface area of 70 cm², resulting in a current density of 0.06 mA/cm² and a charge density of 1.1 C/cm², which are within current safety guidelines (Bikson et al. 2016). The anode electrode will be centered on the interhemispheric fissure and the central sulcus. This area was chosen due to its previous use in fatigue studies using neuromodulation (multiple sclerosis, Ferrucci et al. 2014; fibromyalgia, Altas et al. 2019; Stroke, De Doncker et al. 2021). The motor cortex is being used more often in neuromodulation studies due to its structural and functional connectivity to cortical and subcortical networks/nodes, e.g. basal ganglia, cingulate cortex. The cathodal electrode will be placed on the nonparetic shoulder. Modeling of cephalic and extracephalic tDCS montages indicates that extracephalic placement of the cathode leads to deeper current flow in the somatosensory cortex (Noetscher et al. 2014). The sham tDCS procedure will be performed in the same manner as active a-tDCS, however, the current will be ramped up and down over 30 seconds (Fridricksson et al. 2018). Figure 2 displays the protocol timeline. Days 2-6 will be consecutive, no more than 36 hours will be allowed between treatment visits. If more than 36 hours elapses the participant will be withdrawn from the study. The measurement of state fatigue, via f-VAS, will be performed before and after each tDCS treatment visit. Follow-up assessments of state and trait fatigue will be performed via phone at one (Follow-up 1), two (Follow-up 2), and four weeks post-treatment (Follow-up 3). The primary study outcome will be the comparison of the FSS scores obtain at baseline (Visit 1) and one week post-tDCS (Follow-up 1).

Neuroimaging

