Anatomical and spectroscopic images (T1, T2, ¹H-MRS) will be acquired using the Center for Biomedical Imaging at MUSC's standard imaging protocols. The T1 and T2 images will be used for the computation of stroke lesion locations and volumes. The T1 images will also be used to guide the corticomotor response (CMR) testing listed below. We will use Single-voxel MEGhcher-GArwood Point RESolved Spectroscopy (MEGA-PRESS) ¹H-MRS to assess central nervous system inflammation. Voxels will be placed in the basal ganglia and insular cortex in both hemispheres. Basal ganglia voxels will be placed with the anterior border abutting the anterior portion of the lentiform nucleus and as medial as possible to avoid the ventricles (Pretzsch et al. 2019). The basal ganglia have been previously implicated in fatigue post-stroke (Tang et al. 2010) and in multiple sclerosis (Roelcke et al. 1997, Tellez et al. 2008). The insular cortex is a prominent brain region involved in interoception. Interoception is the sensing, integrating, interpreting and regulating self-signals and has been theorized to contribute to fatigue (Stephan et al. 2016, Enoka et al. 2021) and implicated in fatigue in multiple sclerosis (Gonzalez Campo et al. 2020). Levels of Myo-inositol (MI), total creatine (tCr), and choline (CHO) and their ratios to N-acetylaspartate (NAA) will be quantified as markers of inflammation (reviewed by Chang et al. 2015). Spectroscopy data will be analyzed using the freely available LCModel software as in our previous works (Moss et al. 2018, 2019). Pre and post tDCS intervention spectroscopy values will be compared to determine changes in inflammatory markers associated with the intervention. The measurement of state fatigue will be performed before and after each imaging session.

Blood collection and analysis

Before and after five days of tDCS treatment, participants will provide a blood sample for the measurement of pro-inflammatory cytokines. These cytokines include interleukin- (IL) 1, 6, and 10, tumor necrosis factor (TNF) α , and c-reactive protein. Whole blood will be collected in EDTA-treated tubes and separated into plasma, immune cells (buffy coat), and red blood cells. Separated samples will be frozen and stored until the end of the study. Once all samples are collected they will undergo Simple Plex™ microfluidic ELLA platform immunoassay (ProteinSimple, USA) analysis for listed cytokines (Leligdowicz et al. 2017, Burke et al. 2021). State fatigue will

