
Table 1: Clinical Outcome Measures

Domain	Instrument
Fatigue (State)	Visual Analogue Scale
Fatigue (Trait)	* Fatigue Severity Scale (FSS) (Krupp et al. 1989) Modified Fatigue Impact Scale (mFIS) (Fisk et al. 1994) Fatigue Assessment Scale (FAS) (Michielsen et al. 2003)
Anxiety	Hospital Anxiety and Depression Scale (Zigmond and Snaith 1983)
Depression	Patient Health Questionnaire 9 (PHQ-9) (Spitzer and Williams 1999)
Pain	Defense and Veterans Pain Rating Scale (DVPRS) (Polomano et al. 2016)
Physical Function / Mobility	10 m walk over GAITRite (Kindred et al. 2019)
Community Participation / Quality of Life	Standard Form 36 (Anderson et al. 1996)

* Primary outcome measure for Aim 1

Statistical Analysis

Aim 1 Hypothesis: Five days of a-tDCS applied to the lower extremity motor cortex will result in a reduction of PSF severity in individuals with chronic stroke. A two-factor, between-subjects factor of GROUP (active a-tDCS, sham) and within-subjects factor of TIMEPOINT (pre, post), mixed model ANOVA will be used to test this hypothesis. The primary outcome variable for this analysis is the FSS scores. We will also calculate measures of effect size to power future studies.

Aim 2 Hypothesis: Five days of a-tDCS applied to the lower extremity motor cortex will result in a reduction of inflammatory markers within the central nervous system and the peripheral blood. Pre- and post-intervention markers of inflammation will be compared using a mixed model, two-factor ((between-subjects factor of GROUP (active a-tDCS, sham) and within-subjects factor of TIMEPOINT (pre, post)), ANOVA. Each outcome measure (MI, tCR, IL-1, TNF- α , etc) will be tested independently.

Additional Analyses: Examine the possible relationship between PSF severity and inflammatory markers. This relationship may provide mechanistic insight into the effect of tDCS on PSF and allow us to possibly predict future responders/non-responders to a-tDCS treatments of PSF. Pearson's correlations will be calculated between baseline measures of inflammation and FSS scores to determine a possible role of current state inflammation on PSF severity. Correlations between the change in FSS scores and inflammation, pre- and post-a-tDCS, will be calculated to provide preliminary evidence of a possible mechanism of reduced inflammation and improved PSF.

Potential Problems / Solutions

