Some groups have reported a 50% response rate to tDCS. Due to our small sample, non-responders may reduce our statistical power. A post-hoc response analysis, defined as a change greater than the minimally clinically important difference of 0.45 (Nordin et al. 2016), will be performed to power future studies. Placing the ¹H-MRS voxel within the basal ganglia is a logical starting place based on the published literature. However, it is possible that inflammatory markers outside this region are as influential or more so than basal ganglia measures. Future work may be required to determine which brain regions are best to assess with ¹H-MRS. Another limitation is that only a-tDCS is being tested. Cathodal tDCS (c-tDCS) has been reported to have similar long-term effects on gene expression and protein synthesis. The benefits of tDCS on fatigue, to date, have mostly investigated a-tDCS although future investigations need to determine if c-tDCS may be a viable treatment option. Another area that will need to be addressed in future studies is if our post-intervention measurements of metabolite changes reflect the last episode of treatment or if they are indicative of long-term changes in response to tDCS. Future studies will also need to assess the optimal intervention length and follow-up periods.

Biostatistical Justification

This pilot work is based on a similar study investigating a-tDCS' effects on post-stroke fatigue (De Doncker et al. 2021). The FSS is the primary measure of fatigue severity and the minimally clinically important difference (MCID) was reported to be 0.45 (Nordin et al. 2016), with changes greater than this resulting in reported improvements in QOL. To detect this level of change with 80% power and an alpha = 0.05 between two groups using a within-between-subjects interaction ANOVA a minimum sample of 8 individuals in each group is required. We will enroll 24 participants (12 a-tDCS, 12 sham) to account for any drop-out, loss to follow-up, or complications during data collection. We have projected to perform recruitment and data collection activities over nine months.

REFERENCES

Altas, E. U., Askin, A., Besiroglu, L., & Tosun, A. (2019). Is high-frequency repetitive transcranial magnetic stimulation of the left primary motor cortex superior to the stimulation of the left dorsolateral prefrontal cortex in fibromyalgia syndrome? *Somatosens Mot Res*, 36(1), 56-62.

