The intervention being studied is a five-session anodal transcranial direct current stimulation (tDCS) intervention delivered over five consecutive days. Measures of post-stroke fatigue and inflammation (central inflammation measured by magnetic resonance spectroscopy and peripheral markers measured via blood analysis) will be made before and after the intervention.

Trial Management. The study will be primarily managed from the Functional Neurostimulation Laboratory ([name], PI) within the Division of Physical Therapy within the College of Health Professions at the Medical University of South Carolina. The target population is adults more than six months post-stroke with clinically present fatigue (average Fatigue Severity Scale > 4).

Data Management and Analysis

The primary outcome of the study is the change in post-stroke fatigue severity (fatigue severity scale (FSS), pre- and post-intervention) and markers of central (measured using magnetic resonance spectroscopy (MRS)) and peripheral (measured via blood analysis) inflammatory markers. Analyses will be guided by the specific hypotheses of the study. Post-hoc exploratory analyses will be conducted with two-tailed tests and more conservative statistical procedures which guard against Type I error (e.g., Tukey tests). All primary hypotheses will be tested at level of significance $\alpha=0.05$. We will also estimate the effect sizes of interest and provide 95% confidence intervals for them.

Quality Assurance

Data quality will be monitored by random inspection of the completed forms by research staff/PI.

Regulatory Issues. All unexpected Adverse Events (AEs) will be reported to the MUSC IRB within 10 working days. Serious AEs (SAEs) will be reported within 24-business hours. Follow-up of all unexpected and serious AEs will also be reported to the IRB. All AEs will be reviewed weekly by the PI and yearly by the IRB. Any significant actions taken by the local IRB and protocol changes will be relayed to NIH. AEs and SAEs occurring during the course of the trial will be collected, documented, and reported in accordance with IRB requirements.

Definition of AE and SAE

Adverse events are defined as any untoward medical occurrence that may present itself during treatment or administration of an intervention, and which may or may not have a causal relationship with the treatment.

Serious adverse events are defined as any medical occurrence that:

- Results in death,
- Is life-threatening,

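### Aim 2 markers get a test equivalent to comparing change scores; ANCOVA on the pre-treatment value is a cheap gain, and two points of wording need settling

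*Combined protocol and SAP*

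**What the plan says.** The Statistical Analysis section tests Aim 1 (FSS) with a two-factor model, treatment group by time: "within-subjects factor of TIMEPOINT (pre, post), mixed model ANOVA will be used to test this hypothesis". Aim 2 has the same structure: "Pre- and post-intervention markers of inflammation will be compared using a mixed model, two-factor", with each marker tested separately. Neither paragraph says which term of the model decides the hypothesis, and neither uses the baseline value as a covariate.

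Four other places bear on this:

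- Biostatistical Justification sizes the FSS comparison "using a within-between-subjects interaction ANOVA a minimum sample of 8 individuals in each group is required".
- Study Design and a-tDCS Treatment fixes the FSS time points: "The primary study outcome will be the comparison of the FSS scores obtain at baseline (Visit 1) and one week post-tDCS (Follow-up 1").
- Neuroimaging says "Pre and post tDCS intervention spectroscopy values will be compared to determine changes in inflammatory markers associated with the intervention", and Data Management and Analysis says "The primary outcome of the study is the change in post-stroke fatigue severity (fatigue severity scale (FSS), pre- and post-intervention"). Neither sentence mentions group.
- Potential Problems / Solutions plans, as an aid to powering later studies, "A post-hoc response analysis, defined as a change greater than the minimally clinically important difference of 0.45". It names no time point and no active-versus-sham contrast.

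**The concern.** The main issue is precision. The trial already collects a pre-treatment value of every marker. Subtracting that value, as the interaction test in effect does, is efficient only when pre and post values are highly correlated. At lower correlations it carries baseline noise into the comparison, which matters with 8 to 12 people per arm.

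Two smaller issues concern wording. A two-factor mixed ANOVA yields three tests (group, time, interaction), and only the interaction compares the randomised arms on change. Entry requires an average FSS of at least 4, so some fall is expected in both arms with no treatment effect. A time main effect would count that fall as benefit. The responder count has the same weakness: a proportion improving by more than 0.45 includes retest noise and regression to the mean unless it is set beside the sham proportion.

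**Working it through.** **Inputs from the documents.** 12 per arm enrolled and a minimum of 8 per arm, alpha 0.05 (Biostatistical Justification); FSS entry at 4 or more (Inclusion Criteria); response threshold 0.45. **Not in the documents:** the pre-post correlation r, any SD and any mean. These are assumed and shown as ranges.

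**The plan's own figure.** The 8 per group cannot be reproduced, because 0.45 points comes with no SD of change or correlation. For a two-sided t-test on change with 80% power, 8 per group needs a standardised difference of 1.51, so an SD of change of 0.45/1.51 = 0.30. That is a separate matter; here 8 serves only as the lower end of the number analysed.

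**ANCOVA against change scores.** With unit SD, equal variances and n per arm:

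- change-score difference: variance = 2(1 − r) × 2/n
- ANCOVA difference: variance = (1 − r²) × (2/n) × [1 + 1/(2n − 4)]
- ratio = (1 + r)/2 × [1 + 1/(2n − 4)]

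At n = 12 the bracket is 1 + 1/20 = 1.05. At n = 8 it is 1 + 1/12 = 1.083. For example, n = 12 and r = 0.7 gives 0.85 × 1.05 = 0.892. Power below is change score → ANCOVA, by simulation.

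| Per arm | r | Variance ratio | Power, 0.5 SD effect | Power, 1 SD effect |
|---|---|---|---|---|
| 12 | 0.5 | 0.788 | 21.6 → 26.1% | 64.9 → 75.0% |
| 12 | 0.7 | 0.892 | 32.9 → 36.1% | 85.6 → 89.0% |
| 12 | 0.8 | 0.945 | 45.5 → 47.6% | 95.7 → 96.6% |
| 8 | 0.5 | 0.812 | | 46.0 → 54.3% |
| 8 | 0.7 | 0.921 | | 67.2 → 70.5% |
| 8 | 0.8 | 0.975 | | 83.4 → 84.0% |

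Setting the ratio to 1 gives the break-even: r = 2/1.05 − 1 = 0.905 at 12 per arm and 2/1.083 − 1 = 0.846 at 8. Allowing also for the larger critical t value (2n − 3 against 2n − 2 degrees of freedom), these become 0.89 and 0.82. Above break-even, the largest simulated power loss was 1.7 points at 12 per arm and 3.3 at 8, both at r = 0.98.

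Type I error was 4.9 to 5.2% for both tests with normal data. With untransformed lognormal markers it was 3.5 to 4.7% for ANCOVA and 3.2 to 4.7% for change scores, with variance ratios of 0.61 to 0.88. Skewness therefore did not inflate error in either test.

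**Time main effect with no treatment effect.** FSS was simulated with entry at 4 or more, range 1 to 7, rounded to ninths, 12 per arm. With population mean at least 5 and r at least 0.7 (SD 1.0 to 1.5), a significant fall over time appears in about 4 to 13% of trials, against 2.5% nominal in that direction. It appears more often at lower means or lower r. The interaction rejects in about 5% throughout.

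**Responders with no treatment effect.** Ignoring selection, P(fall > 0.45) = 1 − Φ(0.45/SD of change): 6.7% at SD 0.3, 22.7% at 0.6 and 32.6% at 1.0. With entry at 4 or more and assumed mean 4 to 5.5, SD 1.0 to 1.5 and r 0.5 to 0.95, it is about 5 to 52%. At mean 5, SD 1 and r = 0.85 it is 19% with a mean fall of only 0.04, so mostly retest noise.

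**Precision of the responder difference.** At 12 per arm the 95% half-width is 1.96 × √[2p(1 − p)/12]: 0.30 at p = 0.17 and 0.40 at p = 0.50.

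**The case against.** The strongest reply is that the plan is already sound. The sizing text names the interaction for the FSS, and Aim 2 uses the same model, so the intended test can be read across. The sentences in Neuroimaging and in Data Management and Analysis describe a measurement and an outcome; they are not rival analyses. This largely stands, so naming the term is a clarification. A reader might infer that the trial will be judged on uncontrolled pre-post change, but the documents do not support that: the governing section includes the sham group in both models.

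A reader might also infer that a time main effect would be badly misleading. High rates need a low population mean together with a low r. The criteria also ask for self-reported persistent fatigue for six months, and database candidates are prescreened on a tiredness item. Both favour genuinely high scores and less regression to the mean.

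On ANCOVA, one may say it is a preference: the planned test is valid, and the gain at r = 0.7 to 0.8 is only 1 to 3 points at 12 per arm. It is right that nothing is invalid. But the covariate is already collected, and the possible gain (about 10 points at r = 0.5) exceeds the possible loss.

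On responders, the plan does not confine the analysis to the active arm, and it separately plans effect sizes for future studies and promises confidence intervals for them. It would also be wrong to size a later trial from the remark "Some groups have reported a 50% response rate to tDCS": nothing says that figure is a rate of FSS change above 0.45. What remains is silence on the time point and on the sham contrast.

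**Conclusion.** The point holds as a low-cost improvement, not as an error in the planned test. For Aim 2, ANCOVA cuts the variance of the treatment comparison by about 21, 11 and 5.5% at r = 0.5, 0.7 and 0.8 with 12 per arm. The benefit is close to nil at 8 per arm with r = 0.8, and there is a small loss above the break-even. These figures assume normal data with equal variances, and every r is an assumption. The unnamed interaction and the incompletely defined responder analysis are minor clarifications. Their sizes also rest on assumed means, SDs and correlations.

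**What to change.** **Aim 2.** Replace the mixed ANOVA with wording such as: *Each post-treatment marker will be analysed by ANCOVA with treatment group and its pre-treatment value; the result is the adjusted active-minus-sham difference with 95% CI.*

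**Aim 1.** Either state that the GROUP × TIMEPOINT interaction for FSS at Visit 1 and Follow-up 1 is the test, reported as the active-minus-sham difference in change with 95% CI, or use ANCOVA of Follow-up 1 FSS on Visit 1 FSS, which is an acceptable option. Wherever the mixed ANOVA is kept, say that time main effects and within-arm changes are descriptive.

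**Responders.** Define response as an FSS reduction greater than 0.45 from Visit 1 to Follow-up 1. Report it in both arms with the active-minus-sham difference and 95% CI, as a descriptive supplement to the planned effect size. With a half-width of 0.30 to 0.40 it should not be the sole planning quantity.

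**Cost.** Analysis wording only, with no new data. ANCOVA uses one residual degree of freedom and loses at most about 2 to 3 power points at very high r. None of this resolves the unsupported sample size.

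### Aim 2 tests many inflammatory markers at an unadjusted 0.05, with no lead marker and no rule for how the four MRS voxels enter the two-factor ANOVA

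*Combined protocol and SAP*

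**What the plan says.** The Neuroimaging section states "Voxels will be placed in the basal ganglia and insular cortex in both hemispheres", which makes four voxels per session. It continues: "Levels of Myo-inositol (MI), total creatine (tCr), and choline (CHO) and their ratios to N-acetylaspartate (NAA) will be quantified as markers of inflammation". That is three levels and three ratios. The blood section lists five markers: IL-1, IL-6, IL-10, TNF-α and C-reactive protein.

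Under Statistical Analysis, Aim 2 predicts a reduction in these markers. The analysis is given as "Pre- and post-intervention markers of inflammation will be compared using a mixed model, two-factor" ANOVA. The two factors are group and timepoint, with no term for region or hemisphere. On the unit of testing: "Each outcome measure (MI, tCR, IL-1, TNF- α , etc) will be tested independently".

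The Data Management and Analysis section lists the central and peripheral markers in the primary outcome beside the FSS and tests all primary hypotheses at 0.05. Its safeguard, "more conservative statistical procedures which guard against Type I error (e.g., Tukey tests"), is stated for post-hoc exploratory analyses only. Potential Problems / Solutions speaks of a single spectroscopy "voxel within the basal ganglia is a logical starting place based on the published literature", although the insula is also measured.

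**The concern.** Aim 2 is a directional hypothesis about a class of markers, with no lead marker named. As written, a fall in any one marker, in any one voxel, could be reported as support. The plan does not say whether the four voxels are analysed singly, averaged, reduced to one chosen voxel, or modelled by region and side. With the choice open, it can be made after the results are seen.

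The same gap carries into the planned correlations between change in FSS and change in inflammation, because it is not stated which voxel supplies the MRS value. The Tukey example does not help: it compares means within one outcome and does not control error across markers or voxels.

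**Working it through.** The documents state no number of Aim 2 tests and no error rate for them, so there is no figure of the plan's own to reproduce. The only calculated figure, 8 per group, concerns the FSS and does not bear on this point.

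**Inputs from the documents**
- Voxels per session: 2 regions × 2 hemispheres = 4
- MRS measures per voxel: 3 levels + 3 ratios = 6
- Blood markers: 5
- Level per test: 0.05
- Participants: 12 per group

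**Number of tests**
- Voxel by voxel: 6 × 4 = 24 MRS tests; 24 + 5 = 29 in all
- One value per marker: 6 + 5 = 11

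**Chance of at least one false positive if independent, 1 − 0.95^k**
- k = 29: 1 − 0.95^29 = 0.774; expected false positives 29 × 0.05 = 1.45, whatever the correlation
- k = 24: 1 − 0.95^24 = 0.708
- k = 11: 1 − 0.95^11 = 0.431

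**Falls only.** Aim 2 predicts a reduction, and a two-sided 0.05 test leaves 0.025 for falls.
- k = 29: 1 − 0.975^29 = 0.520; expected 29 × 0.025 = 0.73
- k = 11: 1 − 0.975^11 = 0.243

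**Correlated tests.** The documents give no correlations, so these are assumed. Simulation used 12 per group and t-tests on change scores (equivalent to the group-by-timepoint interaction with two timepoints).
- All 29 tests, with a common correlation among the 24 MRS tests and, separately, among the 5 blood tests: 0.69 at a correlation of 0.3 and 0.42 at 0.7. Falls only, the value drops to about 0.22 at 0.7, against 0.52 if independent.
- The 24 MRS tests alone, one common correlation: about 0.60, 0.48, 0.33 and 0.17 at 0.3, 0.5, 0.7 and 0.9.

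**Ways of using the four voxels for one measure** (simulated, 12 per group)
- Four voxels entered as if they were separate participants: Type I error 12%, 16%, 19% and 22% at between-voxel correlations of change of 0.2, 0.3, 0.4 and 0.5.
- One mean change per participant: 5% at every correlation tried.
- Mixed model with a random participant intercept only, testing the pooled group-by-timepoint term: from below 1% to just over 25%, depending on the voxel-specific variance and the correlation of change. It is therefore not a safe substitute for the mean.

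**Precision of the mean.** With equal voxel variances, the standard error relative to one voxel is √((1 + 3ρ)/4): √(1.6/4) = 0.63 at ρ = 0.2 and √(2.5/4) = 0.79 at ρ = 0.5.

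**The case against.** A reader might infer that the two-factor model forces a choice between 24 separate tests and treating correlated voxels as independent. The documents do not support that. The same ANOVA accepts one value per participant per timepoint, such as a voxel mean or one prespecified voxel. Nor does "will be tested independently" mean that voxels are treated as independent. It refers to outcome measures, and the model has a within-subjects factor. The plan nowhere proposes stacking voxels, so the 12% to 22% figures describe a hypothetical analysis.

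The 77% is also an upper figure. It assumes independence, counts rises as well as falls, and includes five blood tests that have no voxel problem.

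This is a 24-person pilot powered on the FSS, which Table 1 marks as primary for Aim 1. Effect sizes with 95% confidence intervals are already planned. Tukey is given only as an example of a wider class of procedures. The two regions are justified separately in the protocol, so averaging over them is one choice among several, and the documents offer no basis for picking a particular lead marker.

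These points limit the size and urgency of the concern. They do not remove it: the markers are listed as primary at 0.05, the conservative procedures are reserved for post-hoc work, and no rule covers the markers or the voxels.

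**Conclusion.** The point stands as an unspecified step combined with unadjusted testing. With all 29 tests, the chance of at least one false positive is 77% under independence and about 42% to 69% at assumed common correlations of 0.7 to 0.3. Counting falls only, it is about 22% to 52%, from a correlation of 0.7 to independence. Settling the voxel question alone does not cure it, since 11 markers at 0.05 still give 43% (24% for falls only) under independence.

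The test counts follow from the documents; the correlations are assumptions. The documents do not show that voxels will be stacked or that all 24 MRS tests will be run. They leave both possible, and stacking should be ruled out in words. Since this is a pilot with the FSS as its powered outcome, this is a cheap improvement and not a flaw that undermines the trial.

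**What to change.** 1. Before unblinding (in this single-blind trial, before allocation is linked to any marker data), name one lead MRS measure and one lead blood marker. Test these two with Holm at 0.05: the smaller p-value against 0.025 and, if that passes, the other against 0.05. Treat these as the evidence on Aim 2. Report all other markers and voxels as exploratory with 95% confidence intervals. A Bonferroni correction over all 29 tests would instead require 0.05/29 = 0.0017 per test.

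2. For each MRS measure, enter one prespecified value per participant per timepoint, for example the mean over the four voxels, in the planned group-by-timepoint ANOVA. An equivalent mixed model with region and hemisphere is acceptable if it includes a participant-by-timepoint random effect; a random intercept alone is not enough. State that voxels will not be entered as independent units, and use the same value in the correlation analyses. Report region, hemisphere and single-voxel estimates descriptively.

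3. Bring the single-voxel wording in Potential Problems / Solutions into line with the Neuroimaging section.

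The cost is analysis wording only, with no new data or visits. The downside is that an effect confined to one voxel is diluted in the mean, and an effect confined to a non-lead marker becomes exploratory. The descriptive estimates would still show both.

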Prospective participants will be recruited from our bioinformatics enabled post-stroke recruitment database which is maintained by the NIH Center of Biomedical Research Excellence in Stroke Recovery at the Medical University of South Carolina. This database, RESTORE, contains over 1200 individuals post-stroke who have consented to be contacted for research purposes. Veterans from our VA-approved recruitment data have agreed to have their contact information placed in RESTORE and their veteran-status is highlighted. Prospective participants more than six months post-stroke will be identified by their response to question 4 of the Personal Health Questionnaire Depression Scale (PHQ-8) stored in their database record. A response of 2 or 3 indicates "Feeling tired or having little energy" on at least half the days over the last 2 weeks. Veterans who participated in the recently completed VA RR&D sponsored study "Fatigue and Mobility in Stroke: a Biomechanical and Neurophysiological Investigation" (IK1 RX0003126, CDA-1, PI: [name]) will be preferentially contacted and recruited to participate in this project. Initial contact will be made with prospective participants via telephone. The project basics will be explained and interested individuals will be invited to our research laboratory for final eligibility screening and consent. *Full inclusion and exclusion criteria are listed in the "Protection for Human Subjects" section.* Once consented, participants will complete a set of questionnaires to assess levels of state and trait fatigue, depression, anxiety, and pain. State fatigue is defined as a participant's instantaneous perception of fatigue and is measured on a 0-10 visual analogue scale (f-VAS) with 0 signifying no feelings of fatigue and 10 representing the most fatigued an individuals could imagine. Trait fatigue refers to an individual's perception of fatigability, i.e. how fatigue affects their ability to perform activities of daily living and participate in social and physical activities. The most common instrument used to measure trait fatigue is the Fatigue Severity Scale (FSS, Krupp et al. 1997). The FSS is a nine-question, scored on a 1-7 likert scale, self-reported questionnaire assessing the impact of fatigue on a variety of activites over the last seven days. An average score of 4 on the FSS signifies clinically relevant fatigue (total FSS score ≥ 36). Additional clinical tests and questionnaires will be performed to measure physical disability (gait speed), balance, and quality of life. Women of childbearing potential will perform a urinalysis to determine pregnancy status. Pregnant women will be excluded due to unknown effects of tDCS on fetal development and mother's milk. The

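### Is the sample size of 8 per group for a 0.45-point FSS change unsound because its SD and correlation are not stated?

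*Combined protocol and SAP*

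**What the plan says.** The Biostatistical Justification takes its target from the literature: "the minimally clinically important difference (MCID) was reported to be 0.45". It then gives the sample size for 80% power at a 0.05 significance level: "interaction ANOVA a minimum sample of 8 individuals in each group is required". Enrolment is set higher: "We will enroll 24 participants (12 a-tDCS, 12 sham) to account for any drop-out, loss to follow-up, or complications during data collection". The paragraph says that the work builds on a similar tDCS study in post-stroke fatigue, but carries no figure over from it.

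The scale is described under Recruitment and Consent: "The FSS is a nine-question, scored on a 1-7 likert scale, self-reported questionnaire". The inclusion criteria use the average item score (at least 4), so 0.45 is naturally read on the 1-7 average. Study Design and a-tDCS Treatment makes the primary comparison Visit 1 against a telephone assessment one week after treatment. Statistical Analysis tests Aim 1 with a 2 x 2 mixed ANOVA (group by time) and adds: "We will also calculate measures of effect size to power future studies". Data Management and Analysis sets alpha at 0.05 for primary hypotheses, specifies two-tailed tests only for post-hoc analyses, and promises 95% confidence intervals for the effect sizes.

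**The concern.** An interaction sample size needs an SD of change, or a score SD with a pre-post correlation, or a standardised effect with a correlation. None appears anywhere in the document, so the 8 cannot be checked.

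Working backwards makes it look optimistic. The required SD of change is about 0.30 points on a 1-7 self-report scale, between a visit and a telephone call. If the true SD were larger, power for a 0.45-point effect would fall well below 80%. A reader who trusted the stated figure might then take a non-significant result as evidence against an effect of the size of the minimally important difference. This sentence is the only support in the document for the power of the primary test.

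**Working it through.** **Inputs from the plan.** Difference 0.45 points; power 80%; alpha 0.05; minimum 8 per group; 12 per group enrolled. **Not in the plan.** SD, correlation, standardised effect, sidedness, drop-out rate. Any value used for these below is an assumption.

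**1. Can the plan's own figure be reproduced?** Not from the stated inputs alone. For a within-between interaction with two time points, the noncentrality is lambda = f² x N x 2 / (1 - rho), on 1 and N - 2 degrees of freedom. Several assumed pairs return N = 16 (8 per group):

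| Assumed f | Assumed rho | lambda at N = 16 | Power, N = 14 | Power, N = 16 |
|---|---|---|---|---|
| 0.40 | 0.5 | 0.16 x 32 / 0.5 = 10.24 | 78.5% | 84.5% |
| 0.25 | 0.8 | 0.0625 x 32 / 0.2 = 10.00 | 77.5% | 83.6% |
| 0.45 | 0.30 | 0.2025 x 32 / 0.70 = 9.26 | 74.3% | 80.7% |
| 0.45 | 0.35 | 0.2025 x 32 / 0.65 = 9.97 | 77.4% | 83.5% |

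So 8 per group is an attainable output of the named method, but the inputs behind it cannot be identified.

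**2. What does 0.45 raw points require?** In a 2 x 2 mixed ANOVA the interaction test equals a two-sample t-test on change scores, with lambda = (n/2) x d² and d = 0.45 / SD of change. Solving for 80% power:

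| n per group | Sidedness | d needed | Largest SD of change |
|---|---|---|---|
| 8 | two-sided | 1.507 | 0.45 / 1.507 = 0.299 |
| 12 | two-sided | 1.197 | 0.45 / 1.197 = 0.376 |
| 8 | one-sided | 1.308 | 0.45 / 1.308 = 0.344 |
| 12 | one-sided | 1.048 | 0.45 / 1.048 = 0.429 |

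The pairs in step 1 do not corroborate this independently. Any pair giving N = 16 must have nearly the same d. For f = 0.40 and rho = 0.5, for example, d² = 10.24 / 4 = 2.56, so d = 1.60 and the SD would be 0.45 / 1.60 = 0.281.

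**3. What if the SD is larger?** Two-sided power for 0.45 points, by assumed SD of change:

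| Assumed SD | 8 per group | 12 per group |
|---|---|---|
| 0.30 | 80% | 94% |
| 0.35 | 67% | 85% |
| 0.40 | 55% | 75% |
| 0.60 | 29% | 42% |
| 1.0 | 13% | 18% |

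**4. Can the documents say which row applies?** With equal pre and post SDs, the correlation needed is rho = 1 - SD_change² / (2 x SD_score²). At 8 per group and an assumed score SD of 0.5, this is 1 - 0.299² / 0.50 = 0.82; at 0.8 it is 1 - 0.299² / 1.28 = 0.93. The plan gives neither a score SD nor a correlation. The entry criterion confines baseline averages to 4-7, where even a uniform spread has an SD of only 3 / √12 = 0.87. That makes the largest score SDs less likely at baseline, but it does not fix the SD of change.

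**5. Is the feared misreading already guarded against?** The expected 95% interval half-width is 2.145 x √(2/8) = 1.07 SDs of change at 8 per group and 2.074 x √(2/12) = 0.85 at 12. If the observed SD of change exceeds 0.45 / 1.07 = 0.42 (8 per group) or 0.45 / 0.85 = 0.53 (12 per group), even an observed difference of zero leaves 0.45 inside the interval. The planned intervals would therefore show directly when the data cannot exclude the minimally important difference.

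**The case for a change.** The strongest case for a change is that the plan chose to make a formal power claim, so it should be checkable; calling the study a pilot does not excuse an unsupported number. Every raw-points reading leads to a small SD of change, and an assumed score SD of 0.8 needs a correlation of 0.93 between a visit and a telephone call. Potential Problems / Solutions warns that non-responders may reduce power, yet the rise from 8 to 12 is attributed only to losses and data problems. Rewriting one paragraph would cost almost nothing.

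Much of this stands as description. The inputs are missing, the ceiling of about 0.30 is correct under the stated reading, and the paragraph does not show where such an SD would come from. What does not follow is that the sample size is wrong. The cited similar study may supply the SD; that cannot be checked here. The low-power rows rest wholly on assumed SDs, and nothing in the document makes 0.4 or 0.6 likelier than 0.3. If 0.45 was entered as Cohen's f, no SD in points was used at all; the document neither shows nor excludes this. Low cost alone is not a reason to amend when the amendment alters nothing that is done or estimated.

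**Conclusion.** This is a gap in reporting, and no change to the plan follows. The stated 8 per group is unverifiable from the document but not shown to be wrong. It requires an SD of change of at most 0.299 points (two-sided, exact t, raw 0.45-point difference in change), 0.344 if one-sided, and 0.376 two-sided if all 12 per group are evaluable. Whether those values are realistic cannot be judged from the document.

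Writing the inputs down, or restating the sentence as a detectable difference of 1.51 SDs of change at 8 per group and 1.20 at 12, would leave the number enrolled, the visits, the test and the estimate untouched. The plan already limits the harm. It calls itself a pilot, warns that a small sample may cost it power, enrols 12 / 8 = 1.5 times its stated minimum, and commits to effect sizes with 95% intervals. Those intervals, rather than the planned 80%, are what a reader of a non-significant result should use. The conclusion would be different if the document contained an FSS SD of change clearly above these limits; it contains none.
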